Rocuronium – standard dosage

Maintenance: Randomization to 3 groups, with infusion begun after induction while the patient is being prepped. Infusions to run until cardiologist informs anesthesiologist that no further ablations will be performed. Infusions will be prepared by the hospital pharmacy.

- Group 1: Placebo (0.9% NaCL)
- Group 2: Remifentanil 0.25 mcg/kg/min
- Group 3: Remifentanil 0.5 mcg/kg/min

Sevoflurane end-tidal concentration 1 to 4% (equivalent to 0.5 to 2 MAC)

Rocuronium – standard dosage

Ondansetron 0.1 mg/kg following last ablation

Emergence: Prior to emergence from anesthesia, the catheter access sites will be infiltrated with lidocaine as is the usual practice, the catheters removed, muscle relaxation reversed, and the patient allowed to awaken normally from anesthesia. The headphones and probe cap will be removed from the subject's head prior to emergence from anesthesia. The BIS sensor will be removed just before or just after emergence from anesthesia.

The only substantive difference between the study protocol and standard clinical care is the administration of remifentanil. Intravenous opioids are typically not given beyond induction of general anesthesia nor during catheter ablation of the arrhythmia. In this study, there is no reduced pain control than normal.

After the Procedure:

In the recovery room, before the subject is discharged from the hospital, a Post-Operative Questionnaire (Appendix C) will be performed in which the subject is asked about the last thing they remember before going to sleep, the first thing they remember upon waking up, and whether they have any memories or were dreaming during the procedure. If the research team is unable to administer the Post-Operative Questionnaire prior to the subject being discharged from the hospital, the subject will be contacted by telephone to complete this.

Additionally, information pertaining to the study will be collected from the electronic medical record. This information will include data from the pre-operative evaluation, electrophysiology procedure, anesthesia administered, and the recovery period.

b. Patient Selection and Inclusion/Exclusion Criteria

Inclusion Criteria:

12-30 years of age

Scheduled for electrophysiology procedure (EP) under general endotracheal anesthesia

Structurally normal heart by echocardiography

Right-handed

Exclusion Criteria:

Structural heart disease
Left handed
Unable to cooperate or understand the nature of the study

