optical contact with the scalp. The optodes are contained within a cap which will be placed on the patient's head in the catheterization laboratory. The light passes harmlessly through the subject's scalp onto the brain surface and returns, with some attenuation, to the detector optodes. The returning light yields information about blood-oxygenation levels in that region of the brain. The probe cap is not constricting and any discomfort will be minimized by surrounding the optodes with foam tape and using soft cloth straps against the head and face. After initial positioning, the probe may need to be shifted slightly until adequate signal is obtained through all detector fibers. In some cases, hair will be parted in order to achieve better optical contact. There will be no shaving of hair.

Prior to induction of general anesthesia, baseline activation signals of the somatosensory cortices and prefrontal cortices will be obtained in response to finger-tapping and brush stimuli applied to the dorsum of the hand as described above. This will provide baseline information to compare to the signals obtained during the procedure from surgically-induced pain.

In order to activate the Supplemental Motor Area, which should be quiet unless patients move, headphones will be placed on the subjects and an audio recording will be presented to subjects. The prompt will request that the subject imagine squeezing a tennis ball in their right hand, in a clasping motion, without actually performing the action. During this we expect SMA activity to occur if the subject is consciously aware based on similar results from prior studies. The audio stimuli will be presented to the subject every half hour throughout the procedure.

2. Patients will be randomized into one of three groups to receive an infusion which will be started after induction of general anesthesia while the patient is being prepped.

Group 1: 0.9% NaCl infusion

Group 2: Remifentanil 0.25 mcg/kg/min infusion

Group 3: Remifentanil 0.5 mcg/kg/min infusion

The infusions will be prepared by the hospital pharmacy. Investigators performing analysis of the NIRS signals will be blinded to the infusion the patient received. Infusions will be stopped after the cardiologist informs the anesthesiologist that no further ablations will be performed.

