- Postoperative Questionnaire (10 minutes) will be readministered one month following the procedure.

g. Study Timeline (as applicable)

The subject's total time commitment, as detailed above, will be approximately 5 to 6 hours, including the duration of the electrophysiologic procedure. The equipment set up will be done prior to the induction of anesthesia, resulting in no increase in the duration of anesthesia.

In addition, information pertaining to the study will be collected from the electronic medical record. This information will include data from the pre-operative evaluation, electrophysiology procedure, anesthesia administered, and the recovery period.

h. Adverse Event Criteria and Reporting Procedures

Adverse events related to the study will be brought to the immediate attention of the Principal Investigator and the patient's medical and nursing staff. Adverse events would include skin irritation or injury from the optodes and cap straps. Adverse events will be reported by the study investigators to the IRB. Peri-catheterization complications not related to study interventions will not be reported.

5. Data Management and Statistical Analysis

a. Data Management Methods

Boston Children's Hospital is the sole site for enrollment and performance of the study. Research folders will be stored in the Anesthesia Research office in a locked cabinet. NIRS data collected will be stored and analyzed by the P.A.I.N. Group members on this study, either on secure electronic servers or in secure office spaces. Data will be de-identified; any data that is linked to the subject's identity will be kept in a locked cabinet in the Anesthesia Research office and P.A.I.N. group office space.

b. Quality Control Method

Training of all research team members who will operate the TechEn CW7 will be mandatory to ensure the accuracy and reliability of the probe placement and signals acquired. See "Data Analysis Plan" for more details on quantitative analysis.

c. Data Analysis Plan

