d. Statistical Power and Sample Considerations

In our pilot study, we were able to collect useable data from five of the eleven subjects that were enrolled (45%). In the five subjects that produced usable results, the signal of interest had a mean value of -3.764×10^{-7} Moles with a standard deviation of 2.135×10^{-7} Moles. This results in a standardized effect size of 1.763, when using a zero mean for the null case. In order to achieve a 90% power level for this measure, the number of usable data sets is therefore eight. Considering our previous success rate of 45%, approximately 18 subjects will need to be enrolled into each group of the study for a total enrollment of 54 subjects.

e. Study Organization

The principal investigator for this study is [name], MBBCh in the Department of Anesthesiology, Perioperative and Pain Medicine at Boston Children’s Hospital. The Research Nurse(s), Study Coordinator ([name] MPH), and co-investigators ([name] MD, and [name] PhD) are members of the Department of Anesthesiology, Perioperative and Pain Medicine at Boston Children’s Hospital. Other co-investigators ([name] MD) and ([name] PhD) are members of the Department of Cardiology at Boston Children’s Hospital and Martinos Center for Biomedical Imaging, Department of Radiology, Massachusetts General Hospital), respectively. Members of the P.A.I.N. research group will participate in data collection and data analysis.

f. Data and Safety Monitoring Plan

Confidentiality will be ensured by assigning anonymous subject identification codes to each subject. The subject-screening log, which lists the names corresponding to the subject identification codes, will be kept on a locked computer, access to which is limited to only one investigator.

The risk posed to the subject in this study is minimal. Subjects will have the right to discontinue the study at any time prior to induction for any reason. Also, investigators will be in the room ready to stop the experiment in case there is any sort of adverse event. After induction of anesthesia the attending anesthesiologist and/or cardiologist may discontinue the experiment if clinical conditions warrant or in the case of an adverse event. Adverse events will be reported to the IRB as indicated above.

The investigators will review the data after the first 5 subjects and then after every 10 subjects to ensure that adequate data is being obtained.

6. Risks and Discomforts

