DOI: DOI is an investigational tool and though no adverse effects have been reported, it is possible that effects not yet reported may occur. The source lasers used to make the measurements are Class IIIb and use very low power – below the ANSI limit for long-term exposure to infrared light (see chart below). The intensity used to monitor cerebral perfusion

Transmitters: Laser Sources

Number of sources	Up to 32
Type of Source	Lasers Class III b
Source wavelengths	690 and 830 nm
Optical Output Power per source	12 mW, 8 mW
Output control capability	On/Off, Square-wave modulation
Connector type	Optical SMA

parameters is considerably less than the amount of light the brain would receive during an outdoor walk on a sunny day, and therefore is considered to be harmless. Thus far, no hazard to patient, staff or third party has been observed. Should any adverse effects be observed during the study, they will be immediately reported to the IRB.

Operating Room Setting: All of the equipment that is brought into the operating room will follow the standard OR procedures regarding clearance by biomedical engineering and disinfection. Also, after anesthesia is given to the subject the physician or physicians involved in

the procedure reserve the right to discontinue participation in the study for the subject if they feel it is in the subject's best interest.

Side Effects of Remifentanil: Remifentanil differs from the other strong opioids in its rapid onset/offset for all clinical effects, including respiration (Dahan, Niesters et al. 2013). Remifentanil is rapidly metabolized by enzymes within red blood cells after cessation of an infusion. As the elimination half-life is 5-8 minutes and the context sensitive half-life is 2 minutes, increased postoperative sedation from the remifentanil is unlikely and the risk of postoperative nausea and vomiting is low compared to the nausea and vomiting associated with the procedure itself. As part of standard of care, the anesthetic plan includes the administration of ondansetron to reduce post-operative nausea and vomiting.

7. Potential Benefits

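### Reporting of harms from the randomised infusion rests on an undefined case-by-case relatedness judgement, and no comparison of events by arm is planned

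*Combined protocol and SAP*

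**What the plan says.** Section 4.h, Adverse Event Criteria and Reporting Procedures, makes four statements that matter here:

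- Notification: "Adverse events related to the study will be brought to the immediate attention of the Principal Investigator" (the patient's medical and nursing staff are also told).
- The only example: "Adverse events would include skin irritation or injury from the optodes and cap straps".
- Onward reporting: "Adverse events will be reported by the study investigators to the IRB".
- The exclusion: "Peri-catheterization complications not related to study interventions will not be reported".

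Sections 4.a and 4.d both state: "The only substantive difference between the study protocol and standard clinical care is the administration of remifentanil". Section 4.d adds: "Patients will be randomized into one of three groups to receive an infusion which will be started after induction of general anesthesia". One group receives saline and two receive remifentanil.

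Section 6 has a paragraph on remifentanil side effects. It opens with "Remifentanil differs from the other strong opioids in its rapid onset/offset for all clinical effects, including respiration", calls added postoperative sedation unlikely, and calls the risk of nausea and vomiting low compared with that caused by the procedure. A separate paragraph of section 6, on the optical device, says that any adverse effects seen during the study go to the IRB at once.

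Section 5.f rates the risk as minimal, refers back to 4.h for reporting, and schedules reviews after the first 5 subjects and then every 10 to confirm that the data are adequate.

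**The concern.** The adverse-event section is written around the cap and the optodes, while the element that is randomised and departs from usual care is a drug. Events in the laboratory or recovery room can arise from the drug, the procedure or the anesthetic, and a single case often cannot show which. In a trial with a concurrent saline arm, the natural evidence on drug harm is the difference in event frequency between arms, whatever cause was recorded.

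Section 4.h does not use that evidence. It sorts events one at a time by relatedness and drops those assigned to the procedure. The trial could then state that no study-related harm was seen without having compared its arms.

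**Working it through.** The documents give no figure for adverse events, so the check is mainly a comparison of sections.

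**1. Exposure.** Section 5.d says "approximately 18 subjects will need to be enrolled into each group of the study for a total enrollment of 54 subjects". Two of the three groups are allocated to remifentanil: 2 × 18 = 36 of 54. This is the number allocated. Randomisation follows consent (4.a), and some subjects are expected to withdraw or to lack adequate signals, so fewer may receive the drug.

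**2. What 4.h specifies, set against what attribution requires.**

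| Item | In the documents |
|---|---|
| Infusion-related event named as an example | None |
| Criteria for relatedness | None |
| Who judges relatedness | Not stated |
| Whether that person is blinded | Not stated; blinding is described only for the subject and the investigators analysing NIRS signals (4.a, 4.d) |
| Observation window for events | Not stated |
| Summary of events by arm | None in 4.h, 5.c or 5.f |
| Record of early stops of the infusion, by arm | Not required, although 5.f lets the anesthesiologist or cardiologist discontinue |

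**3. Can one event have either cause?** Section 6 itself weighs nausea and vomiting from remifentanil against that from the procedure. So the protocol recognises at least one event type with two possible sources. Under 4.h, the same episode of vomiting is reportable if assigned to the drug and not reported if assigned to the procedure.

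**4. Does another section close the gap?** The broad IRB sentence in section 6 carries no relatedness condition, but it belongs to the device paragraph. Read broadly, it conflicts with the exclusion in 4.h; read narrowly, it does not reach the infusion. Section 5.f sends the reader back to 4.h, and its scheduled reviews concern data adequacy.

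**5. Are the data available?** Yes. Section 4.f says the electronic anesthesia record captures anesthetic and physiologic data. Sections 4.a and 4.g say that procedure, anesthesia and recovery information is taken from the medical record. No definition of harm and no table is linked to them.

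**6. What could a table by arm show?** The documents give no event rates, so these are assumptions. The test is a two-sided Fisher exact test at 0.05, pooled remifentanil (36) against saline (18), with 10% assumed under saline. Power is the sum of the binomial probabilities of all outcome pairs with p ≤ 0.05.

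| Rate under remifentanil | Power |
|---|---|
| 20% | 9% |
| 30% | 32% |
| 50% | 85% |

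Only a very large excess would be detected reliably, so the table is descriptive.

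**The case against.** A reader might infer that the protocol excludes remifentanil harms from reporting. It does not. The example in 4.h is illustrative, the infusion is one of the two study aspects described in 4.d, and the exclusion covers only complications unrelated to study interventions. An event attributed to remifentanil must be reported. This part of the objection stands in full.

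A reader might also infer that the relatedness rule destroys information. The documents do not support that either: the rule governs what is reported, and the anesthesia and recovery records are kept whatever the attribution. Nor do they show that misattribution would in fact occur.

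A third tempting reading is that section 6 lists three harms that 4.h then ignores. Section 6 mentions respiration in a remark about how quickly effects come and go, and plays down sedation and nausea. It does not name haemodynamic events as a remifentanil effect; the case for tabulating them is that physiologic data are already recorded.

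Finally, this is a mechanistic imaging study with no safety objective, investigators are in the room and may stop the experiment, and a safety table would have little power. All true. These points limit the weight of the concern. They do not supply an assessor, a criterion or a comparison with saline, and safeguards for the individual patient do not replace a summary by arm.

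**Conclusion.** The point holds in limited form. Harms of the infusion are formally reportable, but whether a given event is reported depends on a relatedness judgement for which the documents give no assessor, criteria or blinding, and which no planned analysis checks against the saline arm. If the assessor knows the arm, that knowledge can influence attribution; if not, the assessor must judge relatedness without knowing whether the subject received an opioid. Tabulating events from any cause by arm avoids both problems.

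The point bears on 36 of 54 planned subjects by allocation. It rests on reading the broad IRB sentence in section 6 as a statement about the device, which is where it stands. If it is meant to cover the whole study, the result is a conflict with 4.h that still needs resolving. The primary NIRS analysis is unaffected. I would class this as a cheap improvement.

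**What to change.** In 4.h:

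1. State that infusion-related events are adverse events, and say who judges relatedness and whether that person is blinded to arm.
2. Add wording such as: *From the start of the infusion to discharge from recovery, respiratory, sedation, nausea or vomiting and recorded physiologic (including haemodynamic) events, and any early stop of the infusion, will be extracted for every subject from the electronic anesthesia and recovery records, whatever the attributed cause, and tabulated descriptively by arm.*
3. Keep the relatedness condition for individual IRB reports if wished, but reconcile it with the section 6 sentence on immediate reporting of any adverse effects, and carry the result into 5.f.

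No dose or clinical rule changes. The cost is a paragraph of protocol text, one table and a little more data extraction from records already collected. The report should say that, with about 18 subjects per arm, the table is descriptive and that the absence of a visible difference is not evidence of safety.

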Title: Assessing the Cortical Response to Noxious and Auditory Stimuli Using Near Infrared Spectroscopy in Subjects under General Anesthesia

NCT: NCT02703090

Date: May 22, 2018

Title: Assessing the Cortical Response to Noxious and Auditory Stimuli Using Near Infrared Spectroscopy in Subjects under General Anesthesia

Research Question: To determine the utility of functional near infrared spectroscopy (fNIRS) in the objective, quantitative assessment of nociception and anti-nociception (analgesia) in patients under general anesthesia. A secondary question is the use of fNIRS to measure actual or intended movement either spontaneously, in response to pain, and/or in response to auditory stimuli during general anesthesia.

Significance: This study is part of an ongoing project to determine the value of fNIRS/DOI as a tool for measurement of nociception and anti-nociception and monitoring depth of anesthesia to prevent awareness and pain in patients under general anesthesia. NIRS/DOI is capable of continuously monitoring and tomographically imaging changes in oxy- and deoxyhemoglobin concentrations as a result of noxious stimulation.

Design: Prospective cohort study.

Subjects: Pediatric and adult subjects 12-30 years of age (ASA physical status I or II) undergoing routine electrophysiology procedures in the cardiac catheterization laboratory at Boston Children's Hospital will be eligible for enrollment. We plan to study and obtain useful data sets in 45 subjects with structurally normal hearts undergoing catheter ablation of arrhythmias under planned general endotracheal anesthesia.

Parents/guardians of eligible children and adults will be approached for enrollment at the pre-catheterization evaluation

Variables: Changes in oxyhemoglobin and deoxyhemoglobin concentrations measured by NIRS. Functional NIRS, also known as diffuse optical imaging (DOI), will be used to measure (1) the hemodynamic activations in the bilateral somatosensory cortices and the prefrontal cortices in response to the noxious stimulation (pain) associated with catheter ablation of arrhythmias, and whether these activations are reduced or eliminated by remifentanil, and (2) the hemodynamic activations in the supplemental motor area to actual or intended movement either spontaneously, in response to pain, and/or in response to auditory stimuli.

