The only substantive difference between the study protocol and standard clinical care is the administration of remifentanil. Intravenous opioids are typically not given beyond induction of general anesthesia nor during catheter ablation of the arrhythmia.

e. Definition of Primary and Secondary Outcomes/Endpoints

Primary Outcomes:

The primary outcome is the use of NIRS to measure/detect hemodynamic activations in the bilateral somatosensory cortices and the prefrontal cortices in response to the noxious stimulation

(pain) associated with catheter ablation of arrhythmias, and whether these activations are reduced or eliminated by remifentanil.

Secondary Outcome:

The secondary outcome is the use of NIRS to measure hemodynamic activation in the supplemental motor area to actual or intended movement either spontaneously, in response to pain, and/or in response to auditory stimuli.

f. Data Collection Methods, Assessments and Schedule (what assessments performed, how often)

The study will consist of enrollment and a Preoperative Questionnaire at the pre-catheterization work-up, the study protocol during two days if the patient is discharged the same day of the procedure, or three days if the subject is admitted overnight.

Prior to Preoperative Visit:

- Assessment of eligibility criteria

Pre-Operative Visit:

- Presentation of research study, informed consent/assent (20 minutes)
- Preoperative Questionnaire if patient/parents consent/assent (10 minutes)

Day of Procedure:

1) Before Procedure

- Equipment setup (20 minutes). Test run of brush and audio stimuli (10 minutes).
- BIS sensor applied to patient.

2) During Procedure

- Infusion of NaCL or remifentanil started after induction of anesthesia.
- Audio stimuli (5 seconds each) presented to the patient every half an hour.
- Electronic anesthesia record will capture relevant anesthetic and physiologic data. Study Coordinator and/or Research Nurse will document time and duration of ablations, times of catheter insertion and removal, and assure safety of the patient
- An investigator will operate the NIRS equipment.
- NIRS cap with optodes will be removed from the patient just prior to emergence from anesthesia.
- Average duration of an electrophysiologic study with catheter ablation of arrhythmias is 3 to 4 hours.

3) After Procedure

- Postoperative Questionnaire (10 minutes) will be administered before subject is discharged from the hospital, either on the day of or day following the procedure.

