The NIRS instrument will acquire raw data from each detector at ~40 kHz. The individual signals will then be bandpass filtered. Next, the time series pairs from each detector will be converted from wavelength (absorption) to relative concentrations (of oxy-/deoxy-hemoglobin). This will be done with the modified Beer-Lambert Law and the absorption coefficients of oxy- and deoxy-hemoglobin (HbO and Hb, respectively). (The near-IR wavelengths are chosen because oxy-/deoxy-Hb are the predominant absorbers in the tissue at these wavelengths.) The result will be an oxy-Hb and deoxy-Hb time series associated with each source-detector pair.

For each stimulation run, each smoothed oxy-/deoxy-hemoglobin time series will be examined for periodic amplitude fluctuations. Expected fluctuations include heart rate (~1-3 Hz), breathing and/or “v-waves” (~0.1Hz), as well as any fluctuations induced by the experimental paradigm. If the former sources of noise are substantial, an attempt will be made to filter out these fluctuations (in Fourier space). Any analysis of filtered data will be compared to an analysis of the corresponding non-filtered data. The oxy-hemoglobin portion of the experimentally-induced changes are expected to be 4-9 sec out of phase with the paradigm onsets and offsets (as seen in fMRI work as well as in prior optical recordings).

The data analysis will first be performed on a within-subject basis. Then, the original raw optical time series will be averaged across subjects (for corresponding optode placements only, standardized relative to the EEG 10-20 system).

The biological basis for the signals measured by the optical technique is the same as the basis for fMRI and PET scanning. The regions to be sampled in these pilot studies will be several times larger than single voxels in fMRI scanning. Furthermore, experiments with similar optical instruments indicate that these instruments are at least as sensitive as fMRI. With larger sampling regions (up to a factor of 5 or more), and assuming only comparable sensitivity, the optical imaging should require no more subjects than an fMRI study, and perhaps fewer. Furthermore, optical recording can provide 10-100 times the temporal resolution of fMRI. So, since an optical time series would seem to be at least as good as that coming from an individual voxel (or small collections of voxels) from fMRI data, similar group sizes should be adequate for optical experiments (Boas, Dale et al. 2004).

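### Section 5.c controls systemic noise only by frequency filtering, so a non-periodic, ablation-locked cardiac change that is not caused by pain could contribute to the signal the primary outcome attributes to noxious stimulation

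*Combined protocol and SAP*

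**What the plan says.** Section 4.e defines the primary outcome as detecting "hemodynamic activations in the bilateral somatosensory cortices and the prefrontal cortices in response to the noxious stimulation" of ablation, and then "whether these activations are reduced or eliminated by remifentanil". The synopsis (Variables) makes the same attribution: the activations are those "in response to the noxious stimulation (pain) associated with catheter ablation of arrhythmias".

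Section 5.c describes the noise handling in two steps:

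- Before conversion to haemoglobin concentrations: "The individual signals will then be bandpass filtered". No cut-offs are given.
- After conversion, each series "will be examined for periodic amplitude fluctuations". The expected ones are heart rate (about 1-3 Hz), breathing or v-waves (about 0.1 Hz), "as well as any fluctuations induced by the experimental paradigm". If the first two are substantial, "an attempt will be made to filter out these fluctuations (in Fourier space". Paradigm-induced changes are not filtered, since they are the signal sought.

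The plan compares filtered with non-filtered results and expects the oxy-haemoglobin response 4-9 s after paradigm onsets and offsets.

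Three other elements bear on the point. Section 1 says that randomisation to placebo or one of two opioid doses should help separate cortical activation from scalp sympathetic changes in response to pain. Section 2 lists short-distance probes among the features of the CW 7 device. Section 4.f states: "Electronic anesthesia record will capture relevant anesthetic and physiologic data". It also has staff record the time and duration of ablations. Section 5.c uses neither the physiologic data nor the short-distance probes.

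**The concern.** NIRS measures haemoglobin in the tissue the light crosses, so it responds to systemic circulatory changes as well as to local cortical activity. The stimulus here is delivered to the heart. If rate, rhythm or pressure shifts when ablation starts, for reasons unrelated to pain, the resulting haemoglobin change has the same timing as the response the study looks for. It is not an oscillation at a known frequency, and averaging across subjects does not remove a change that is locked to the stimulus and has a consistent direction.

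At stake is the first half of the primary outcome: whether the placebo-arm signal is a nociceptive cortical response at all. A positive finding could be partly cardiac. An artefact in the opposite direction could instead mask a true response.

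**Working it through.** **Inputs from the documents.** Section 5.d: pilot mean -3.764×10^-7, SD 2.135×10^-7, null mean zero, 90% power, 8 usable data sets, 45% yield, 18 per group, 54 in total. Section 5.c: noise bands of about 1-3 Hz and about 0.1 Hz. Alpha is not stated; two-sided 0.05 is assumed.

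**Step 1. The plan's own figure.** Standardised effect = 3.764 / 2.135 = 1.763, as stated. An exact two-sample t test at two-sided 0.05 needs 8 per group (power 90.6%). A one-sample t test against zero, the null named in the text, needs 6 (power 92.7%). Enrolment: 8 / 0.45 = 17.8, so 18 per group, and 3 × 18 = 54. The figures reproduce and are not in dispute. What matters here is that zero is the only null value the plan states: a consistent non-zero shift from any source would count against it.

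**Step 2. Does the described Fourier filter remove a one-off shift?** Illustration with assumed settings: a 300 s series sampled at 10 Hz; a unit shift starting at 100 s, smoothed with a 5 s time constant; added oscillations at 1.3 Hz and 0.1 Hz. All content at 1-3 Hz and 0.08-0.12 Hz is set to zero. The measure is the mean from 9 s after onset to the end of the shift, minus the mean of the preceding 30 s.

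| Shift length (assumed) | True shift | After filtering | Retained |
|---|---|---|---|
| 30 s | 0.9616 | 0.9609 | 99.93% |
| 60 s | 0.9840 | 0.9836 | 99.96% |
| 120 s | 0.9926 | 0.9918 | 99.92% |

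The shift passes almost intact. A bandpass with a high enough lower cut-off could attenuate it, but would also attenuate a sustained pain response. With no cut-off stated, the plan cannot be credited with that protection.

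**Step 3. What would an artefact do to a test against zero?** Suppose there is no cortical response, but an artefact equal to a fraction f of the pilot mean, with the pilot SD. For a one-sample t test with n = 8 (7 degrees of freedom, two-sided 0.05), the noncentrality is f × 1.763 × √8 = f × 4.987. The probability of reporting activation is:

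| f (assumed) | 0 | 0.1 | 0.25 | 0.5 | 0.75 | 1.0 |
|---|---|---|---|---|---|---|
| Probability | 5% | 7% | 19% | 57% | 89% | 99% |

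The documents do not say where on this scale the trial would lie. The table shows how sensitive the conclusion is, not how large the bias is.

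**Step 4. What does randomisation cover?** Section 1 aims it at sympathetic scalp changes that pain causes. A change caused directly by ablation is a different source. If it is additive and the same in every arm, it cancels on average from a difference between arms, which is real protection for the dose contrast. It does not cancel from the placebo arm's comparison with zero. It would also remain in the remifentanil arms, where it could be read as activation that was not eliminated.

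**The case against.** The strongest reply is that the plan does not accept every signal.

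- The outcome is confined to somatosensory and prefrontal regions, placements are matched to the 10-20 system, and a 4-9 s lag is expected.
- Section 3 reports that pilot ablation signals resembled pain responses in volunteers and on fMRI.
- All signals are bandpass filtered, and the device has short-distance probes. Appendix A is listed but not reproduced in the public text and may say more.
- A dose-related fall under remifentanil would be evidence against a purely cardiac explanation.
- No passage says that rate, rhythm or pressure changes at the moment of ablation, how often, or in which direction.

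Much of this stands. A reader might infer that whatever haemoglobin change coincides with ablation will be labelled pain; the region limits and expected lag do not support so absolute a reading. A reader might also infer that the remifentanil comparison is invalid. That does not follow either, because an artefact unrelated to pain and common to all arms would tend to cancel between them.

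The gap in 5.c remains. Region and lag are expectations, and no rule rejects a signal that departs from them. A pressure change could share the timing. The resemblance to volunteer data is reported, but no test of it is planned. The pre-induction comparators (rest, audio and, if time allows, finger tapping and brushing) all come before general anaesthesia, and none is a circulatory control.

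**Conclusion.** The concern holds as an uncontrolled possible bias. Followed as written, section 5.c would let a non-periodic, ablation-locked systemic change through to the analysis, and it makes no use of the recorded physiology or the short-distance probes that could reveal one. The exposure lies mainly in the claim that the placebo-arm signal is nociceptive; the dose contrast is partly protected.

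Its size is unknown. The probabilities above rest on assumed artefact fractions, the pilot SD and two-sided 0.05; the filter result rests on assumed shift lengths and time constant. That ablation produces such a change is itself a plausible assumption, not something the documents report.

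A reader might go further, express the pilot mean as a small percentage of tissue haemoglobin, and conclude that a trivial blood-volume change explains the pilot effect. The documents do not support that. They give no tissue haemoglobin value and do not say whether the pilot signal is oxy- or deoxy-haemoglobin. The pilot mean is also negative, so a mimic would have to move in that direction consistently across subjects. A small signal does not show that an artefact reaches it.

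This is a worthwhile, cheap improvement to the analysis plan, not a flaw that invalidates the design.

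**What to change.** Add to section 5.c a prespecified adjusted analysis of each ablation window, with these nuisance regressors:

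1. heart rate, taken from the NIRS pulse before that band is filtered out, or from the anesthesia record;
2. recorded arterial pressure, where its time resolution allows (the documents do not state the resolution);
3. short-distance-channel signals, where available.

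Report this beside the unadjusted analysis, in the same way that the plan already compares filtered with non-filtered data. Any claim of a nociceptive cortical response should state whether the response persists after adjustment. Give the bandpass cut-offs in the same paragraph.

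Comparison with non-ablation windows of the same recording that show similar heart-rate or pressure changes can be exploratory where such windows exist. It should not be a decision rule: the documents do not establish that matched windows will occur, and only about 8 usable data sets per group are expected.

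Cost: analysis time, plus aligning the anesthesia record and the logged ablation times with the NIRS clock. No new equipment or patient procedure is needed for heart rate, which the plan already expects to see in the NIRS signal. The downside is that pain itself can change heart rate and pressure, so adjustment may remove part of a true response. That is why both versions should be reported and neither read alone.
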